9.3 Schedule of Activities

The Schedule of Activities (see [Appendix A: Schedule of Activities](#)) shows the timing of planned study procedures. Every effort should be made to adhere to this procedure schedule and all assessments should be completed at each study visit.

9.3.1 Pre-Screening Visit

To minimize Screen failures, there will be an optional Pre-Screening visit which will enable the subject to have a HemoCue Hb prior to proceeding with full Screening. Subjects will need to sign an abbreviated Pre-Screening informed consent form or full consent form prior to Pre-Screening. If the Pre-Screen HemoCue Hb is <10.0 g/dL, the investigative site may proceed with SV1, which preferably will occur on the same day as Pre-Screening.

9.3.2 Screening Visits

Subjects will need to sign a full consent form prior to SV1 procedures. The consent form may be signed in advance of SV1 procedures. The Screening period starts at the time the informed consent is signed and will be a maximum of 8 weeks in duration. Two Screening visits (SV1 and SV2) must be performed within 8 weeks prior to dosing (Baseline visit or Day 1). There must be a minimum of 4 days between the 2 Screening visits and a minimum of 4 days between SV2 or last retest and the Baseline visit.

The Investigator will maintain a log of subjects (both Pre-Screened and Screened) and indicate who of the Pre-Screened subjects was brought in for informed consent and Screening and who of the Screened subjects were enrolled or excluded and the reason for exclusion.

After obtaining informed consent subjects will undergo a number of Screening activities.

9.3.2.1 Screening Visit 1 (SV1)

At SV1, the following activities/procedures will be performed:

- Informed consent (including an additional optional consent for blood samples for future genetic analyses)
- Review of eligibility criteria
- Vital signs including heart rate and blood pressure (assessed in seated position after 5 minutes of rest and prior to blood draws)
- Laboratory procedures:
 - CBC (without differential)
 - Iron indices
 - Folate and vitamin B₁₂ levels
 - Serum Chemistry and eGFR
 - Liver Function Tests
- Visit Registration in IWR

Refer to [Sections 7.4.1, Retesting](#) and [7.4.2, Rescreening](#) for further details regarding repeating laboratory measurements during the Screening period.

9.3.2.2 Screening Visit 2 (SV2)

At SV2, the following activities/procedures will be performed:

- Review of eligibility criteria
- Physical examination
- Demographics and medical history
- Vital signs including heart rate and blood pressure (assessed in seated position after 5 minutes of rest and prior to blood draws), as well as height and weight
- Laboratory procedures:
 - CBC (without differential)
- Serum pregnancy test for females of childbearing potential (eligible subjects will be advised to use an adequate contraceptive method)
- Prior and current medication use

The mean of 2 Hb values from the central laboratory must be <10.0 g/dL to qualify for inclusion into the trial. If the subject's Hb does not qualify after SV1, SV2, or retest Hb, the subject should be considered a Screen failure.

9.3.2.3 Subject Retesting

Subjects who initially fail to qualify for the study based on laboratory test results may be retested once within the 8-week Screening period, per Investigator discretion ([Section 7.4.1, Retesting](#)).

9.3.3 Subject Rescreening

Subjects who fail to meet the qualifying criteria for Hb or eGFR during the Screening period may be considered for rescreening at the discretion of the Investigator if it is felt that the subject's status has progressed and that the subject may now qualify for the study. Additionally, subjects who fail to qualify for the study based on low TSAT, ferritin, folate, or B₁₂ values may be considered for rescreening after receiving replacement therapy. Screening is limited to 3 attempts (Screening and 2 additional rescreening attempts) ([Section 7.4.2, Rescreening](#)).

9.3.4 Baseline Visit (Day 1)

The Baseline visit must be performed at a minimum of 4 days from the last Screening visit (SV2) procedure, including retest(s).

At the Baseline visit, the following activities/procedures will be performed:

- Randomization
- 12-lead ECG (prior to vital sign assessments and blood draws).
- Vital signs including heart rate and blood pressure (assessed in seated position after 5 minutes of rest and prior to blood draws)
- Laboratory Procedures:
 - Random spot urine sample for uACR
 - Coagulation Tests
 - CRP
 - CBC (including differential)
 - Reticulocyte count
 - Serum chemistry and eGFR
 - Liver function tests
 - Iron indices
 - Lipid profile
 - EPO
 - Biomarkers
 - PK (see [Section 9.2.2, Laboratory Evaluations](#); samples to be drawn only for subjects randomly assigned to vadadustat)
 - Exploratory samples
- Review of medical history for new conditions since Screening visit
- Medication use since Screening visit
- Study medication assessments and procedures:
 - Subject will take their first dose of study medication at the investigative site during the Baseline visit
 - Hb by HemoCue for dose initiation
 - Vadadustat dispensing
 - Darbepoetin alfa dispensing

- Oral iron supplementation as needed to maintain ferritin ≥ 100 ng/mL or TSAT $\geq 20\%$ (per local product label; see [Section 8.4.6, Iron Supplementation](#))
- AE assessment as needed (after receiving the first dose of study medication)
- Visit Registration in IWR

9.3.5 Year 1 Treatment Period Visits (Day 2 through Week 52)

During the Year 1 Treatment Period Visits at Weeks 2, 4, 6, 8, 10, 12, 16, 20, 24, 28, 32, 36, 40, 44, 48, and 52, the following activities/procedures will be performed:

- Vital signs including heart rate and blood pressure (assessed in seated position after 5 minutes of rest and prior to blood draws)
- Weight (Weeks 12, 24, 36, and 52)
- Laboratory procedures:
 - Random spot urine sample for uACR (Weeks 28 and 52)
 - CBC (Weeks 2, 4, 6, 8, 10, 12, 16, 20, 24, 28, 32, 36, 40, 44, 48, and 52; differential at Weeks 28 and 52)
 - Reticulocyte count (Weeks 4, 12, 28, and 52)
 - Serum chemistry (Weeks 28 and 52)
 - Serum creatinine and eGFR (Weeks 4, 8, 12, 20, 36, and 44; also at Weeks 28 and 52 as part of the serum chemistry)
 - Liver function tests (Weeks 4, 8, 12, 16, 20, 24, 28, 36, 44, and 52)
 - Iron indices (Weeks 4, 8, 12, 20, 28, 36, 44, and 52)
 - Lipid profile (Weeks 28 and 52)
 - EPO (Weeks 4, 12, 28, and 52)
 - CRP (Weeks 28 and 52)
 - Biomarkers (Weeks 12, 28, and 52)
 - PK (Weeks 4, 12, 28, and 52; see [Section 9.2.2, Laboratory Evaluations](#); samples to be drawn only for subjects randomized to vadadustat)
 - Exploratory samples (Weeks 28 and 52)
- Record date and time of subject's last dose of vadadustat prior to the PK sample (Weeks 4, 12, 28, and 52)
- Safety assessments:
 - AE assessment
 - RBC transfusions and ESA rescue
 - Therapeutic phlebotomy
 - MACE endpoint questionnaire
- Medication assessments and procedures:
 - Review of concomitant medications
 - Hb by HemoCue for dose adjustment
 - Drug reconciliation: Study medication (vadadustat or darbepoetin alfa) reconciliation will be conducted per the pharmacy manual instructions.
 - Vadadustat dispensing as needed per [Section 8.2.1, Dispensing of Vadadustat](#)
 - Darbepoetin alfa dispensing
 - Iron supplementation as needed to maintain ferritin ≥ 100 ng/mL or TSAT $\geq 20\%$ (per local product label; see [Section 8.4.6, Iron Supplementation](#))

- Question subject regarding dosing compliance and whether they have questions or have experienced any problems related to the dosing of study medication (vadadustat or darbepoetin alfa)

- Visit Registration in IWR

9.3.6 Year 2-4 Monthly Hb Monitoring

- Monthly monitoring of Hb as part of local standard of care labs or at unscheduled visits for dose adjustment.

9.3.7 Year 2 Treatment Period Visits (Weeks 53 through 104)

During the Year 2 Treatment Period Visits at Weeks 64, 76, 88, and 104, the following activities/procedures will be performed:

- Vital signs including heart rate and blood pressure (assessed in seated position after 5 minutes of rest and prior to blood draws)
- Weight (Week 104)
- Laboratory Procedures:
 - Random spot urine sample for uACR (Week 104)
 - CBC (Weeks 64, 76, 88, and 104; differential at Weeks 76 and 104)
 - Serum chemistry (Weeks 76 and 104)
 - Serum creatinine and eGFR (Weeks 76 and 104 as part of the serum chemistry)
 - Liver function tests (Weeks 64, 76, 88, and 104)
 - Iron indices (Weeks 64, 76, 88, and 104)
 - CRP (Week 104)
 - Biomarkers (Week 104)
 - Exploratory samples (Week 104)
- Safety Assessments
 - AE assessment
 - RBC transfusions and ESA rescue
 - Therapeutic phlebotomy
 - MACE endpoint questionnaire
- Medication assessments and procedures:
 - Review of concomitant medications
 - Hb by HemoCue for dose adjustment
 - Drug reconciliation: Study medication (vadadustat or darbepoetin alfa) reconciliation will be conducted per the pharmacy manual instructions.
 - Vadadustat dispensing as needed per [Section 8.2.1, Dispensing of Vadadustat](#)
 - Darbepoetin alfa dispensing
 - Iron supplementation to maintain ferritin ≥ 100 ng/mL or TSAT $\geq 20\%$ (per local product label; see [Section 8.4.6, Iron Supplementation](#))
 - Question subject regarding dosing compliance and whether they have questions or have experienced any problems related to the dosing of study medication (vadadustat or darbepoetin alfa)
- Visit Registration in IWR

9.3.8 Year 3/4 Treatment Period Visits (Weeks 116 through 208)

During the Year 3/4 Treatment Period Visits at Weeks 116, 128, 140, 156, 168, 180, 192, and 208, the following activities/procedures will be performed:

- Vital signs including heart rate and blood pressure (assessed in seated position after 5 minutes of rest and prior to blood draws)
- Weight (Weeks 156 and 208)
- Laboratory Procedures:
 - Random spot urine sample for uACR (Weeks 156 and 208)
 - CBC (Weeks 116, 128, 140, 156, 168, 180, 192, and 208; differential at Weeks 128, 156, 180, and 208)
 - Serum chemistry including serum creatinine and eGFR (Weeks 128, 156, 180, and 208)
 - Liver function tests (Weeks 116, 128, 140, 156, 168, 180, 192, and 208)
 - Iron indices (Weeks 116, 128, 140, 156, 168, 180, 192, and 208)
 - CRP (Week 156)
 - Biomarkers (Week 156)
 - Exploratory samples (Week 156)
- Safety assessments:
 - AE assessment
 - RBC transfusions and ESA rescue
 - Therapeutic phlebotomy
 - MACE endpoint questionnaire
- Medication assessments and procedures:
 - Review of concomitant medications
 - Hb by HemoCue for dose adjustment
 - Drug reconciliation: Study medication (vadadustat or darbepoetin alfa) reconciliation will be conducted per the pharmacy manual instructions.
 - Vadadustat dispensing as needed per [Section 8.2.1, Dispensing of Vadadustat](#)
 - Darbepoetin alfa dispensing
 - Iron supplementation to maintain ferritin ≥ 100 ng/mL or TSAT $\geq 20\%$ (per local product label; see [Section 8.4.6, Iron Supplementation](#))
 - Question subject regarding dosing compliance and whether they have questions or have experienced any problems related to the dosing of study medication (vadadustat or darbepoetin alfa)
- Visit Registration in IWR

9.3.9 End of Treatment (EOT) Visit

The EOT visit will be performed at the time a subject permanently discontinues study medication or for subjects on study medication at the time of notification of global study completion (See [Appendix A: Schedule of Activities](#)).

At the EOT visit, the following activities/procedures will be performed:

- Vital signs including heart rate and blood pressure (assessed in seated position after 5 minutes of rest and prior to blood draws), as well as weight
- Laboratory Procedures:

- Random spot urine sample for uACR
- CBC (without differential)
- Serum chemistry including serum creatinine and eGFR
- Liver function tests
- Iron indices
- Biomarkers
- CRP
- Exploratory samples
- Safety assessments:
 - AE assessment
 - RBC transfusions and ESA rescue
 - Therapeutic phlebotomy
 - MACE endpoint questionnaire
- Recording of concomitant medications
- Drug reconciliation: Study medication (vadadustat or darbepoetin alfa) reconciliation will be conducted per the pharmacy manual instructions.
- Question subject regarding dosing compliance and whether they have experienced any problems related to the dosing of study medication (vadadustat or darbepoetin alfa)
- Visit Registration in IWR

9.3.10 Follow-Up Visit

The follow-up visit will be conducted in person or via the telephone 4 weeks after the EOT visit. The following activities/procedures will be performed:

- AE assessment
- RBC transfusions and ESA rescue
- Therapeutic phlebotomy
- MACE endpoint questionnaire
- Recording of concomitant medications

9.3.11 Unscheduled Visits

Unscheduled assessments may be conducted at any time as medically warranted. The following activities/procedures will be performed. At a minimum,

- MACE Endpoint Questionnaire
- AE assessments
- Any other procedures that are medically warranted at the discretion of the Investigator

9.3.12 End of Study Subject Status

The End of Study (EOS) assessment documents the subject status at the global study completion or at the time of subject withdrawal of consent or when subject is deemed LTFU or upon death. The table below outlines how to handle each subject based on their status.

The following activities/procedures will be performed. At minimum,

- EOS subject status

Subject Status	Global Study Completion
Subject on Study Medication (includes those on temporary interruption) at time of global study completion	
 • Perform EOT visit • Perform the Follow-up visit 4 weeks after EOT and include EOS subject status
Subject permanently discontinued study medication and continues to be followed in the study	
Optimal data collection would include the following assessments:
 
 • EOS subject status (must collect at minimum) • MACE Endpoint Questionnaire • AE Assessment 
NOTE: EOT and the Follow-up visit 4 weeks after EOT to be performed at time study medication is permanently discontinued.

Subject Lost to Follow-up	
Work with third party vendor to ascertain vital status and complete EOS subject status
 
If subject-site contact is reestablished and possible, collect available information for EOS subject status.

Subject Withdrawn Consent	Complete the EOS subject status form at the time of withdrawal of consent, absolute refusal of ALL methods of MACE and health status follow-up.
Subject Death	Complete the EOS subject status form at the time of death (see Section 10 Adverse Events for more details on other actions related to reporting a death).

9.4 Study Medication Stopping Rules

Study medication must be permanently discontinued if a subject meets one of the criteria in Table 2 below

Table 2. Study Medication Stopping Rules

ALT or AST >3x ULN and total bilirubin >2x ULN	Permanently Discontinue Treatment
ALT or AST >3x ULN and INR >1.5	Permanently Discontinue Treatment
ALT or AST >8x ULN	Permanently Discontinue Treatment
ALT or AST remains >5x ULN over 2 weeks *	Permanently Discontinue Treatment

ALT or AST >3x ULN with symptoms including e.g., fatigue, nausea, vomiting, right upper quadrant pain, fever, rash or eosinophilia	Permanently Discontinue Treatment
--	-----------------------------------

* Re-challenge generally should be avoided with ALT or AST >5 times ULN unless there are no other good therapeutic options.

ALT: alanine transferase; AST: asparagine transferase; INR: international normalized ratio; ULN: upper limit of normal

See Section 10.1.1, Adverse Events for reporting requirements related to a subject being permanently discontinued based on meeting the laboratory abnormalities list above in [Table 2](#).

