	
interval must be observed prior to restarting vadadustat after the last dose of rescue medication, and treatment may be resumed after the following intervals:
 
 • 2 days after last dose of epoetin rescue • 7 days after last dose of darbepoetin alfa rescue • 14 days after last dose of methoxy polyethylene glycol-epoetin beta rescue. 
Following ESA rescue, the study medication should be resumed at the same dose as previously used or one dose higher and adjusted according to the Dose Adjustment Algorithms.
 
2. RBC Transfusion: Investigators will use their local institution’s transfusion guidelines when determining whether to transfuse a study subject. In general, in the event of an acute or severe loss of blood, a RBC transfusion should be administered as clinically indicated. In less severe instances but where there may be worsening of anemia or moderate to severe symptoms of anemia, RBC transfusions are permitted at the discretion of the Investigator given the medical necessity. Reasons for RBC transfusion will be captured in the appropriate CRF. Study medication (vadadustat or darbepoetin alfa) may be continued during the transfusion period.

Phlebotomy	
If a subject’s Hb exceeds 14.0 g/dL or the rate of rise of Hb raises concern to the Investigator, the subject may be phlebotomized based on the Investigator’s judgment. The method of phlebotomy will be in accordance with the investigative site’s standard clinical practice.

Study Medication Stopping Rules	
Study medication must be permanently discontinued if a subject meets one of the criteria.
 
 • ALT or AST >3x Upper Limit of Normal (ULN) and total bilirubin >2x ULN • ALT or AST >3x ULN and INR >1.5 • ALT or AST >8x ULN • ALT or AST remains >5x ULN over 2 weeks* • ALT or AST >3x ULN with symptoms (e.g., fatigue, nausea, vomiting, right upper quadrant pain, fever, rash) or eosinophilia 
*Re-challenge generally should be avoided with ALT or AST >5x ULN unless there are no other good therapeutic options.

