Point of care Hb: Using HemoCue[®], Hb will be monitored throughout the study to determine if the dose of study medication (vadadustat or darbepoetin alfa) will be adjusted, interrupted, or maintained as described in [Section 8.4.4, Dosing and Dose Adjustment Guidelines](#).

- Reticulocyte count: An automated reticulocyte count (both absolute and percent) will be performed at Baseline and at Weeks 4, 12, 28, and 52.
- Coagulation tests: Blood samples will be drawn at Baseline to assess the prothrombin time (PT), partial thromboplastin time (PTT), and international normalized ratio (INR).
- Folate and Vitamin B₁₂: Blood sample will be drawn at SV1 to assess the folate and Vitamin B₁₂ levels.
- Urine albumin-to-creatinine ratio (uACR): A random urine spot sample should be collected at the investigative site during the Baseline, Weeks 28, 52, 104, 156, 208 and EOT to assess the uACR. Subjects should refrain from heavy exercise 24 hours before the test.
- C-reactive protein (CRP): A blood sample for CRP will be collected at Baseline, Weeks 28, 52, 104, 156, and EOT.
- Serum Chemistry: Blood samples to assess serum chemistry will be collected at SV1, Baseline, and twice annually at Weeks 28, 52, 76, 104, 128, 156, 180, 208, EOT. At all other noted visits in [Appendix A: Schedule of Activities](#), serum creatinine and eGFR will be performed only at Weeks 4, 8, 12, 20, 36, 44. The serum chemistry will include the following assays: sodium, potassium, bicarbonate, chloride, calcium, magnesium, phosphorus, glucose, creatinine, blood urea nitrogen (BUN), creatine phosphokinase (CPK), uric acid, albumin, total protein, and eGFR calculation.

Note: When a $\geq 50\%$ decline in eGFR from the Baseline value is observed, a repeat central laboratory measure should be performed within 30 to 60 days.

- Liver Function Tests: Blood samples to assess liver function will be collected at SV1, Baseline, Weeks 4, 8, 12, 16, 20, 24, 28, 36, 44, 52, 64, 76, 88, 104, 116, 128, 140, 156, 168, 180, 192, 208, and EOT. Liver function tests will include: total bilirubin, alkaline phosphatase, ALT/SGPT, AST/SGOT, and lactate dehydrogenase (LDH).
- Iron indices: Blood samples to assess the iron indices will be collected at SV1, Baseline, Weeks 4, 8, 12, 20, 28, 36, 44, 52, 64, 76, 88, 104, 116, 128, 140, 156, 168, 180, 192, 208, and EOT. Assessments will include the following indices: ferritin, iron, TIBC, and TSAT.

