If new elevations in ALT or AST >3 times ULN, **without** an elevation of total serum bilirubin >2 times ULN are identified, the following steps are to be taken:

- Temporary discontinuation of Investigational Medicinal Product (IMP);
- Repeat testing of ALT, AST, ALP, and total bilirubin, should be completed within 48 to 72 hours to confirm the abnormalities and to determine trend;
- IMP should not be resumed until monitoring indicates abnormalities have resolved or have stabilized.

Details on the management of subjects with other ALT and AST abnormalities are further described in [Section 9.4, Study Medication Stopping Rules](#).

Worsening of Anemia – In this study, it is possible that some subjects may experience a worsening of anemia. As the primary endpoint of this study assesses Hb response, worsening of anemia is captured as part of this efficacy parameter. Worsening of anemia should not be

considered an AE unless the worsening of anemia is associated with a cause *other than* the subject's CKD.

Transplantation – During this long-term study, it is anticipated that some subjects may receive a kidney transplant. These events will not be recorded as AEs. Subjects will discontinue study medication for receipt of a kidney, other solid organ, hematopoietic stem cell or bone marrow transplant and should continue with the Schedule of Activities and safety assessments as described in [Section 7.5.5.2, Permanent Discontinuation of Study Medication](#).

Malignancy – During this long-term study, some subjects may develop a newly diagnosed malignancy or a recurrence of a malignancy. At the discretion of the Investigator, these subjects may continue study medication (vadadustat or darbepoetin alfa). For reporting of adverse events of malignancy, see [Section 10.1.2 Serious Adverse Events](#).

Renal-Related Events - Some subjects will experience a progression of their CKD over the course of this study as part of the natural course of the disease. In addition, the study population is prone to experience acute, transient loss of kidney function of different etiologies, sometimes concomitantly complicated by progression of CKD.

To ensure consistent reporting of renal events, the following guidelines are to be used when reporting a renal-related AE:

- The following situations **should always be reported as SAEs** with seriousness criterion “medically important,” if no other seriousness criteria are met (see Section 10.1.2, Serious Adverse Events):

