- [d] An abbreviated ICF will be used for Pre-Screening. If the subject is eligible for Screening, a separate full ICF will be used, which may be signed in advance of the SV1 procedures. The Screening period starts at the time the informed consent is signed and will be a maximum of 8 weeks in duration. An additional optional consent form for collection of blood samples for future genetic analysis will be provided at SV1.
- [e] If the Pre-Screen HemoCue Hb is <10.0 g/dL, the investigative site may proceed with Screening Visit 1 (SV1), preferably on the same day as Pre-Screening.
- [f] Inclusion/Exclusion criteria will be reviewed at the Pre-Screening and Screening visits (SV1 and SV2). Final eligibility determination will occur following the Screening visits when all data are available.
- [g] Vitals: Heart rate and blood pressure to be assessed in the seated position after 5 minutes of rest. Height (SV2 only) and weight (SV2, Weeks 12, 24, 36, and 52, yearly thereafter, and at the EOT visit) will also be measured.
- [h] Physical exam: a physical exam is required at SV2 as outlined in the protocol. Thereafter, an abbreviated symptom-directed physical exam should be performed at the discretion of the Investigator as clinically indicated.
- [i] ECG should be performed prior to blood draws when possible and obtained after the subject has been resting comfortably in a supine position for approximately 5 minutes
- [j] Serum pregnancy will be tested in women of childbearing potential at SV2. (Eligible subjects will be advised to use an adequate contraceptive method.) Additional serum or local urine pregnancy tests should be conducted throughout the study in sufficient number, as determined by the Investigator or required by local regulations, to establish the absence of pregnancy during the study. If positive at SV2, the subject is not eligible to enter the study. If a subject becomes pregnant during the study, the subject must permanently discontinue study medication and should attend all subsequent study visits and be continually monitored according to the Schedule of Activities for the duration of the study.
- [k] Subjects may be retested and/or rescreened as detailed in [Section 7.4, Retesting and Rescreening](#).
- [l] Coagulation tests: prothrombin time (PT), partial thromboplastin time (PTT), and international normalized ratio (INR).

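### The INR liver-stopping rule is mandatory, but the protocol requires no INR after Baseline, not even in the repeat panel triggered by ALT/AST >3x ULN

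*Protocol*

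**What the plan says.** All references are to the current protocol, Amendment 7 (Version 8).

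- **The rule.** The synopsis states: "Study medication must be permanently discontinued if a subject meets one of the criteria". Table 2 in Section 9.4 lists five criteria, and one of them is "ALT or AST >3x ULN and INR >1.5".
- **When INR is measured.** Section 9.2.2: "Coagulation tests: Blood samples will be drawn at Baseline to assess the prothrombin time (PT"; the same sentence goes on to name PTT and INR. Footnote [l] of Appendix A defines the row: "Coagulation tests: prothrombin time (PT), partial thromboplastin time (PTT), and international normalized ratio (INR". That row has a single mark, at Baseline.
- **What the liver panel contains.** Section 9.2.2: "Liver function tests will include: total bilirubin, alkaline phosphatase, ALT/SGPT, AST/SGOT, and lactate dehydrogenase (LDH".
- **What follows a new ALT/AST elevation.** For ALT or AST above 3x ULN without "an elevation of total serum bilirubin >2 times ULN are identified, the following steps are to be taken", Section 10.1.1 orders three steps: a temporary stop, then "Repeat testing of ALT, AST, ALP, and total bilirubin, should be completed within 48 to 72 hours", then a condition on restart: "IMP should not be resumed until monitoring indicates abnormalities have resolved or have stabilized".
- **Reporting.** Section 10.1.1 also has new ALT/AST elevations above 3x ULN reported as SAEs to the Medical Monitor or CRO designee within 24 hours. The Amendment 7 change table shows the second condition: no other cause has been identified.

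**The concern.** A stopping rule worded as mandatory needs an input that the protocol makes sure is collected. Here the input is INR, and nothing after Baseline requires it. The rule is checked only if the investigator thinks to order the test.

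The gap falls where the result matters most. When bilirubin is above 2x ULN, another row of Table 2 already ends treatment. When it is not, INR can be the one finding that separates a temporary hold from permanent discontinuation, and the repeat panel for exactly that situation leaves INR out.

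What is at stake is re-exposure of a subject whose liver synthetic function may be impaired, and uneven handling of the same case across approximately 390 sites. It is a patient-safety matter. It does not touch the efficacy or MACE conclusions: Section 11.5 keeps data collected after study-medication discontinuation in both primary analyses.

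**Working it through.** No sample-size, power or alpha figure is involved, so the check is a trace of where INR is required, set beside where the rule needs it.

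**1. Scheduled liver panels after Baseline (Section 9.2.2).**
- Year 1: Weeks 4, 8, 12, 16, 20, 24, 28, 36, 44, 52 = 10
- Year 2: Weeks 64, 76, 88, 104 = 4
- Year 3: Weeks 116, 128, 140, 156 = 4
- Year 4: Weeks 168, 180, 192, 208 = 4
- EOT = 1
- Total: 10 + 4 + 4 + 4 + 1 = 23

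Each measures total bilirubin, alkaline phosphatase, ALT, AST and LDH. None measures INR.

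**2. Scheduled INR after Baseline.** The Baseline list (Section 9.3.4) includes coagulation tests. The lists for Year 1, Year 2, Years 3/4, EOT and Follow-up (Sections 9.3.5, 9.3.7 to 9.3.10) do not. Count: 0.

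**3. Triggered INR.** The repeat panel in Section 10.1.1 names four analytes: ALT, AST, ALP and total bilirubin. Count of INR: 0.

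**4. Does the protocol require what each Table 2 row needs after Baseline?**

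| Table 2 row | Input beyond ALT/AST | Required after Baseline? |
|---|---|---|
| >3x ULN and bilirubin >2x ULN | bilirubin | Yes, scheduled and repeat panels |
| >3x ULN and INR >1.5 | INR | No |
| >8x ULN | none | Yes |
| >5x ULN over 2 weeks | none | Yes, through repeat ALT/AST |
| >3x ULN with symptoms or eosinophilia | symptoms; eosinophils | Yes, through AE questioning at each visit and a CBC differential at 8 scheduled visits (Weeks 28, 52, 76, 104, 128, 156, 180, 208) |

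One row of five rests on a test that is never required after Baseline. The eosinophil count is not tied to the trigger either, but it is at least scheduled.

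**5. Who depends on INR alone?** Remove everyone caught by the other four rows. What remains is a subject with ALT or AST >3x to 8x ULN, not above 5x ULN over 2 weeks, bilirubin not above 2x ULN, no listed symptoms and no eosinophilia. For this subject an INR above 1.5 means permanent discontinuation, and an INR at or below 1.5 means possible restart.

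**6. Can that subject be restarted without an INR?** Section 10.1.1 bars resumption until the abnormalities have resolved or stabilized, and an unmeasured INR is not visible as an abnormality. Section 7.5.5.1 favors resuming treatment unless it is contraindicated, and asks for Medical Monitor contact before resumption only when the interruption exceeds 60 days. The SAE report is a notification: it does not order an INR and does not make restart wait for a review. So the answer is yes.

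**The case against.** The case against has several strands, and part of it stands.

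- **Investigators can order the test.** Section 9.3.11 allows any medically warranted procedure at an unscheduled visit, and a rule keyed to INR tells a careful investigator what to check. This stands. A reader might infer that the rule cannot operate at all; the protocol does not support that. It supports only that the rule's input is left to discretion.
- **The subject is off drug and the sponsor knows.** Treatment is held at once. Unexplained cases are reported within 24 hours, Section 10.3.3 requires follow-up information within 24 hours of awareness, and the subject is monitored until the condition resolves or stabilizes. This stands, and it rules out any inference of continued exposure or of restart out of the sponsor's sight. It does not supply the missing result.
- **The residual group is narrow.** It is. Fatigue counts as a symptom in Table 2 and is also a listed symptom of the anemia under treatment (Section 8.4.7.1), so some of these subjects may already stop under the symptom row.
- **A required INR brings its own problem.** Anticoagulated subjects are not excluded. Exclusion 10 covers only DVT or PE within 12 weeks before randomization, and the Amendment 3 entry in Appendix F says chronic anticoagulation for older events is allowed. Table 2 has no exception for them, so a therapeutic INR above 1.5 would force permanent discontinuation. This stands, and the fix has to deal with it.

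A reader might also infer that the hold-and-resume steps in Section 10.1.1 contradict Section 9.4, because they exempt only the bilirubin combination, while ALT or AST above 8x ULN, or above 3x ULN with symptoms or eosinophilia, can also require permanent discontinuation. The text does not support a contradiction. Directly after those steps, Section 10.1.1 refers to Section 9.4 for other ALT and AST abnormalities, Section 7.5.5 does the same, and Section 9.4 is worded as an obligation.

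**Conclusion.** The point holds in a limited form. One of the five mandatory liver-stopping criteria depends on a test that is required 0 times after Baseline, against 23 scheduled liver panels and a triggered repeat panel of 4 analytes that also leaves it out. The consequence is confined to restart after a hold, in the narrow group described in step 5 of the working.

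The conclusion rests on the protocol as written fixing which analytes are drawn. Section 9.2.2 mentions separate laboratory instructions, but only for collection, processing and shipment. The protocol gives no frequency of ALT/AST above 3x ULN and none of INR above 1.5 among such subjects, so the number affected cannot be estimated. Nothing here changes the power, the alpha, the sample size or the primary analyses. It is a modest patient-safety correction worth making, since Amendment 7 was itself issued on guidance about drug-induced liver injury.

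**What to change.** In Section 10.1.1:

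1. Add PT/INR to the 48 to 72 hour repeat panel triggered by ALT or AST above 3x ULN.
2. Require that the INR result be available and checked against Table 2 before study medication is resumed.
3. State, there or in Section 9.4, how an INR above 1.5 explained by therapeutic anticoagulation is handled. One option is to compare it with the subject's Baseline INR and have the Medical Monitor review the case before a decision.

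No change to the hold-and-resume wording is needed beyond this, and no INR needs to be added to the routine visit schedule.

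The cost is one more analyte on a draw the protocol already requires, a short wait for its result before restart, and a rule for anticoagulated subjects. Sample size, power and alpha stay as they are.
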